4 STUDY DESIGN

4.1 Overall Design

This is a two-center, stratified and randomized, four period, two arm crossover, non-inferiority trial to demonstrate that BrachyGel Vaginal Hydrogel Packing System is non-inferior to standard method vaginal packing (standard).

Two sites are included in the trial design in order to reflect the most common applicators used in intracavitary cervical cancer brachytherapy:

- Tandem and ovoid brachytherapy+/- interstitial needles (UVA cohort)
- Tandem and ring-based brachytherapy +/- interstitial needles (AHN cohort)

The BrachyGel Hydrogel Vaginal Packing System will be compared to gauze packing and/or rectal retractor packing per the institution's standard of care packing practice.

Participants will be stratified by site (UVA/AHN) and randomized to either Arm A or Arm B. Fraction 1 for all participants (both Arms) will be according to standard of care packing and fractions 2-5 (periods 1-4) will alternate between standard of care and BrachyGel packing, as shown in *Figure 1*.

4.2 End of Study Definition

Primary completion date is the date that the final participant was examined or received an intervention for the purposes of final collection of data for the primary outcome, whether the clinical study concluded according to the pre-specified protocol or was terminated.

Study completion date is the date the final participant was examined or received an intervention for purposes of final collection of data for the primary and secondary outcome measures and adverse events (for example, last participant's last visit), whether the clinical study concluded according to the pre-specified protocol or was terminated.

5 STUDY POPULATION

5.1 Inclusion Criteria

In order to be eligible to participate in this study, an individual must meet all of the following criteria:

1. Biopsy showing cancer of the cervix (squamous cell carcinoma, adenocarcinoma, adenosquamous, neuroendocrine, etc)

- 2. FIGO IB1 IVB Staging according to FIGO and TNM guidelines
- 3. Planning to receive brachytherapy as a part of the definitive treatment for cervical cancer

Version Date: 11/16/2021

- 4. Karnofsky performance status (KPS) ≥ 70 or ECOG status ≤1
- 5. Stated willingness to comply with all study procedures and availability for the duration of the study
- 6. Age ≥ 18 years
- 7. Agreement to adhere to Lifestyle Considerations (see *section 5.3*) throughout study duration

5.2 Exclusion Criteria

An individual who meets any of the following criteria will be excluded from participation in this study:

- 1. History of pelvis or abdominal radiation therapy (RT) that is not a part of the definitive treatment plan for the cancer of interest"
- 2. History of total or partial hysterectomy
- 3. Plan to receive external beam RT (EBRT) alone as the definitive treatment plan for the cancer of interest
- 4. Known pregnancy or lactation (no pregnancy test required prior to participation)
- 5. Known contraindications to brachytherapy

5.3 Lifestyle Considerations

During this study, women of childbearing potential are required to use highly effective contraception methods following study entry and through the last fraction of brachytherapy.

Women of childbearing potential (WOCBP) includes any female who has experienced menarche and who has not undergone successful surgical sterilization (hysterectomy, bilateral tubal ligation or bilateral oophorectomy) or is not postmenopausal (defined as amenorrhea ≥ 12 consecutive months; or women on hormone replacement therapy (HRT) with documented serum follicle stimulating hormone level > 35 mIU/mL).

The following birth control methods are allowed during the study:

- 1. Barrier methods
 - a. Diaphragm with spermicide
 - b. Cervical cap with spermicide
 - c. Condom with spermicide

2. Hormonal methods

- a. Hormonal contraceptives (such as the birth control pill)
- b. Intra-uterine device (IUD)
- 3. Abstinence (no heterosexual activity)

5.4 Screen Failures

Screen failures are defined as participants who consent to participate in the clinical trial but are not subsequently randomly assigned to the study intervention or entered in the study. A minimal set of screen failure information is required to ensure transparent

BrachyGel, RadOnc 003

reporting of screen failure participants, to meet the Consolidated Standards of Reporting Trials (CONSORT) publishing requirements (for NIH studies) and to respond to queries from regulatory authorities. Minimal information includes demography and any serious adverse event (SAE).

Version Date: 11/16/2021

Individuals who do not meet the criteria for participation in this trial because of a modifiable factor may be rescreened.

6 STUDY INTERVENTION

6.1 Description of Study Intervention(s)

Participants will be assigned to Arm A or Arm B, as described in section 4.1 and Figure 1. Fraction 1 for all participants (both Arms) will receiving standard of care packing. During fractions 2-5 of brachytherapy, participants will have vaginal packing alternating between the BrachyGel Vaginal Hydrogel Packing System and standard of care vaginal packing, strategy which will include gauze vaginal packing or rectal retractor.

For Arm A of the study, the BrachyGel Packing System will be used during fractions 3 and 5. Standard packing will be used for fractions 1, 2 and 4.

For Arm B of the study, the BrachyGel Packing System will be used during fractions 2 and 4. Standard packing will be used for fractions 1, 3 and 5.

6.2 Dosing and Administration

6.2.1 Dose Delays

Delays in brachytherapy fractions will be according to institutional guidelines.

6.3 Preparation/Handling/Storage/Accountability

6.3.1 Acquisition and Accountability

The investigational devices will be stored in a secure area. Each package of the Brachygel Vaginal Hydrogel Packing System will be single-use specific to a particular participant and any remaining packs will be destroyed in accordance with institutional policies, as directed by Brachyfoam.

6.3.2 Appearance, Packaging, and Labeling

Details on the appearance, packaging and labeling may be found in the clinical use instructions provided. The device will be labeled in accordance with 21 CFR 812.5 and will include the following information: lot number, quantity of contents, name and place of business of the manufacturer, packer or distributor, and the required investigational device statement ("CAUTION: --Investigational device. Limited by Federal (or United States) law to investigational use"). The labeling will also include relevant contraindications, hazards, adverse effects, interfering substances or devices, warnings or precautions.

6.3.3 Product Storage and Stability

The device will be stored by the study team at a temperature between 35 and 72 degrees Fahrenheit (2 and 22 degrees Celsius). The product is stable with these conditions for at least 6 months after manufacture.

Version Date: 11/16/2021

6.3.4 Preparation

Please see the clinical use instructions provided for this information.

6.4 Registration and Randomization

All participants must sign the consent form prior to determination of eligibility for this study.

When a site is ready to enroll a patient, the following documentation must be scanned and emailed to the UVA Coordinating Center:

- Patient and staff signed signature page of the current informed consent form (ICF)
- Completed Inclusion/Exclusion checklist demonstrating subject eligibility
- Supporting documentation needed to confirm eligibility (lab results, scan results etc.)

Consult the Study Reference Manual for instructions on sending this information. The Coordinating Center will consult with the Overall Study PI if questions arise in confirming eligibility. The UVA Coordinating Center will communicate the subject number and arm assignment to the enrolling site.

Registration will occur following verification of eligibility by the treating physician. Eligibility confirmation and registration can occur after the 1st brachytherapy fraction but must occur before the 2nd brachytherapy fraction.

Participants who are consented and accrued to the study should be registered in the designated EDC System in accordance with the Clinical Trial Management System Policy. General guidelines are available in the User Manual and Data Entry Guide.

Participants should receive their first fraction of brachytherapy within 14 days of registration.

Randomization will be discussed with participants during the process of informed consent, and informed consent must be documented prior to randomization. Randomization will be stratified by institution, and will be based on equal allocation between arms. The randomization sequences will be generated by the study statisticians and loaded into RAND and accessed in the designated EDC System. Randomization will occur no sooner than 10 days prior to the second fraction of brachytherapy.

This study does not involve any blinding or masking procedures. Participants will be told which arm they are assigned to.

6.5 Concomitant Therapy

For this protocol, a prescription medication is defined as a medication that can be prescribed only by a properly authorized/licensed clinician. Medications to be reported in

the Case Report Form (CRF) are medications used for pain control for each brachytherapy procedure.

Version Date: 11/16/2021

6.5.1 Rescue Medicine/Supportive Care

Supportive care should be according to institutional guidelines.

7 STUDY CLOSURE, STUDY INTERVENTION DISCONTINUATION AND PARTICIPANT DISCONTINUATION OR WITHDRAWAL

7.1 Study Discontinuation and Closure

This study may be temporarily suspended or prematurely terminated if there is sufficient reasonable cause. Written notification, documenting the reason for study suspension or termination, will be provided by the suspending or terminating party to the investigator, funding agency, and regulatory authorities. If the study is prematurely terminated or suspended, the Principal Investigator (PI) will promptly inform the Institutional Review Board (IRB) and will provide the reason(s) for the termination or suspension. Study participants will be contacted, as applicable, and be informed of changes to study visit schedule

Circumstances that would warrant termination or suspension include, but are not limited to:

- Determination of unexpected, significant, or unacceptable risk to participants
- Insufficient compliance to protocol requirements
- Data that are not sufficiently complete and/or evaluable
- Determination that the primary endpoint has been met
- Change in funding status

If the study is halted due to safety concerns, protocol compliance and/or data quality, the study may resume once these concerns are addressed and satisfy the IRB and Data and Safety Monitoring Committee.

Participants receiving the study intervention at the time of study discontinuation should complete procedures described in section 7.3.

7.2 Participant Discontinuation/Withdrawal

Participants are free to withdraw from participation in the study at any time upon request.

A participant's study treatment would be discontinued for the following reasons:

- Pregnancy
- Significant study intervention non-compliance
- Severe, CTCAE Grade ≥ 4 adverse event considered at least possibly related to the packing procedure
- Participant is unable to receive further brachytherapy due to an adverse event or a change in status (e.g. decline due to disease, change in goals of care, development of metastases).
- Participant decision to withdraw from study treatment and/or the study

The reason for participant discontinuation or withdrawal from study treatment will be recorded on the case report form. Participants that withdraw from study treatment only, will continue with study follow-up. Participants that withdraw from study treatment and study follow-up will not be contacted for any further study visits.

Version Date: 11/16/2021

7.3 Procedures for Discontinuation of Study Intervention

Discontinuation from brachytherapy according to the study does not mean discontinuation from the study, and remaining study procedures should be completed as indicated by the study protocol. If a clinically significant finding is identified (including, but not limited to changes from baseline) after enrollment, the investigator or qualified designee will determine if any change in participant management is needed. Any new clinically relevant finding will be reported as an adverse event (AE).

The data to be collected and procedures to be completed at the time of study intervention discontinuation are included in the schedule of assessments in *section 13.1*.

8 STUDY ASSESSMENTS AND PROCEDURES

8.1 Clinical Assessments

8.1.1 Physical Exam

A complete physical exam will be completed at screening. Karnofsky performance status (KPS) or ECOG status will be collected at the time of each physical exam.

8.1.2 Assessment of Adverse Events

Each participant will be evaluated by a licensed clinician at each study visit. The NCI Common Terminology Criteria for Adverse Events (CTCAE) version 5 will be used for the characterization and grading of adverse events.

8.2 Participant Reported Outcomes

Participant-reported discomfort during both standard and BrachyGel packing placement/removal will be assessed following fractions 2-5 of brachytherapy. See *section* 13.3 for the questions included. The participant will either be given a paper survey of the questions to complete or a member of the clinical or study team will read the questions and possible responses to the participant and the responses will be recorded at that time. The questions must be answered directly following the completion of brachytherapy within 1 hour of removal of packing.

If the participant is sedated for a particular brachytherapy fraction, the participant will not complete the participant discomfort survey questions for that fraction.

8.3 Physicist and Physician Assessments

Physician & physicists will evaluate imaging properties, completeness of packing and general experience of using each packing systems (both standard of care and Brachygel)

following fractions 2-5 for each participant. Only the dosimetry measurements will be collected for the first fraction. See *sections* 13.2 and 13.4 for the instruments.

Version Date: 11/16/2021

9 DATA AND SAFETY MONITORING PLAN

9.1 Adverse Events and Serious Adverse Events

9.1.1 Definition of Adverse Events (AE)

For the purposes of this protocol, we define an adverse event to be any untoward medical occurrence associated (at least possibly related) with the use of the study intervention(s)

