9.1.3.2 Relationship to Study Intervention

All adverse events (AEs) must have their relationship to study intervention assessed by the clinician who examines and evaluates the participant based on temporal relationship and his/her clinical judgment. The degree of certainty about causality will be graded using the categories below. Relationship of the adverse event to brachytherapy and packing system will be assessed separately. In a clinical trial, the study product must always be suspect.

- Definitely Related There is clear evidence to suggest a causal relationship, and
 other possible contributing factors can be ruled out. The clinical event, including
 an abnormal laboratory test result, occurs in a plausible time relationship to study
 intervention administration and cannot be explained by concurrent disease or other
 drugs or chemicals. The response to withdrawal of the study intervention
 (dechallenge) should be clinically plausible. The event must be pharmacologically
 or phenomenologically definitive, with use of a satisfactory rechallenge procedure
 if necessary.
- Probably Related There is evidence to suggest a causal relationship, and the
 influence of other factors is unlikely. The clinical event, including an abnormal
 laboratory test result, occurs within a reasonable time after administration of the
 study intervention, is unlikely to be attributed to concurrent disease or other drugs
 or chemicals, and follows a clinically reasonable response on withdrawal
 (dechallenge). Rechallenge information is not required to fulfill this definition.
- Possibly Related There is some evidence to suggest a causal relationship (e.g., the event occurred within a reasonable time after administration of the trial medication). However, other factors may have contributed to the event (e.g., the participant's clinical condition, other concomitant events). Although an AE may rate only as "possibly related" soon after discovery, it can be flagged as requiring more information and later be upgraded to "probably related" or "definitely related", as appropriate.

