- Unlikely to be related A clinical event, including an abnormal laboratory test result, whose temporal relationship to study intervention administration makes a causal relationship improbable (e.g., the event did not occur within a reasonable time after administration of the study intervention) and in which other drugs or chemicals or underlying disease provides plausible explanations (e.g., the participant's clinical condition, other concomitant treatments).
- **Not Related** The AE is completely independent of study intervention administration, and/or evidence exists that the event is definitely related to another

etiology. There must be an alternative, definitive etiology documented by the clinician.

Version Date: 11/16/2021

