9.1.5 Time Period and Frequency for Event Assessment and Follow-Up

The occurrence of an adverse event (AE) or serious adverse event (SAE) may come to the attention of study personnel during study visits and interviews of a study participant presenting for medical care, or upon review by a study monitor.

All AEs including local and systemic reactions not meeting the criteria for SAEs will be captured on the appropriate case report form (CRF). Information to be collected includes event description, time of onset, clinician's assessment of severity, relationship to study product (assessed only by those with the training and authority to make a diagnosis), and time of resolution/stabilization of the event. All AEs occurring while on study must be documented appropriately regardless of relationship. All AEs will be followed to adequate resolution.

Any medical condition that is present at the time that the participant is screened will be considered as baseline and not reported as an AE. However, if the study participant's condition deteriorates at any time during the study, it will be recorded as an AE.

Changes in the severity of an AE will be documented to allow an assessment of the duration of the event at each level of severity to be performed. AEs characterized as intermittent require documentation of onset and duration of each episode.

Version Date: 11/16/2021

Study staff will record all reportable events with start dates occurring any time after brachytherapy fraction 2 is completed until 30 days (for non-serious AEs) or anytime (for SAEs considered related to the study intervention) after the last day of study treatment. At each study visit, the investigator will inquire about the occurrence of AE/SAEs since the last visit. Events will be followed for outcome information until resolution or stabilization.

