9.1.6 Adverse Event Reporting

AEs must be recorded into the EDC system designated by the University of Virginia database, per the following guidelines.

Table 3

| | Reporting req | uirements f | or AEs that oc | Table 3: High R ccur within 30 da | | se of protocol s | pecified treatme | nt |
|----------------------------------|-------------------|-------------|----------------|--------------------------------------|----------------------|-------------------------|----------------------|---------------------|
| | Grade 1 | Grade 2 | | Grade 3 | | | | Grade 4 & 5 |
| | Expected | | | Expected | | Unexpected | | Expected |
| | and Unexpected | Expected | Unexpected | Without hospitalization | With hospitalization | Without hospitalization | With hospitalization | and Unexpected |
| Unrelated Unlikely | 30 days | 30 days | 30 days | 30 days | 15 days | 30 days | 15 days | 7 days |
| Possible Probable Definite | 30 days | 30 days | 15 days | 30 days | 15 days | 7 days | 7 days | (24-hrs)* 7 days |

^{*}Enter into Cancer Center database within 24 hours if unexpected and definitely related to protocol specified treatment Hospitalization defined as an inpatient hospital stay or prolongation of a hospital stay equal to or greater than 24 hours

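### Section 9.1.1 makes relatedness part of the AE definition, but 9.1.5, Table 3 and 7.3 do not, so the plan leaves open which events enter the secondary safety comparison by packing type

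*Combined protocol and SAP*

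**What the plan says.** - **9.1.1** defines an AE, for the whole protocol, as "any untoward medical occurrence associated (at least possibly related) with the use of the study intervention(s".
- **9.1.3.2** states "All adverse events (AEs) must have their relationship to study intervention assessed by the clinician who examines and evaluates the participant". The grades run down to an unlikely category and an unrelated one, the latter beginning "The AE is completely independent of study intervention". Relationship to brachytherapy and to the packing system is judged separately.
- **9.1.5** says "All AEs occurring while on study must be documented appropriately regardless of relationship".
- **9.1.6** says "AEs must be recorded into the EDC system designated by the University of Virginia database, per the following guidelines". The guidelines are Table 3, whose first row reads "Unrelated Unlikely | 30 days | 30 days | 30 days" and continues with deadlines for the higher grades.
- **7.3** has a newly identified, clinically relevant finding reported as an AE, with no condition on relationship.
- **9.1.7** asks for serious events whether or not they are thought related. **9.1.2**, however, builds the definition of a serious event on an AE or suspected adverse reaction.
- **Section 3** makes the occurrence, intensity and duration of AEs over fractions 2 to 5 a secondary endpoint, to estimate the difference in safety between packings. **10.6** summarizes AEs by packing type. Neither says whether all events or only related ones are meant.
- **6.4** states that nothing is blinded.

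**The concern.** If relatedness is part of the definition, an event judged unrelated is not an AE. The instruction to document regardless of relationship, the first row of Table 3 and the lowest causality grade would then have little or nothing to apply to. All of this is current text. A site working from 9.1.1 and a site working from 9.1.5 could build different AE datasets from the same participants.

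The stake is the between-packing safety comparison. Section 2.2.5 says the device has not been used in living humans, so its AE profile is part of what the trial should establish. Section 2.3.1 describes urinary, bowel and vaginal events after brachytherapy itself, so the cause of a given event will often be a judgement. The clinician making that judgement knows which packing was used. If the judgement decides whether an event is recorded at all, attribution can differ by packing even where true rates do not. Section 11.4 adds that an investigator who founded the manufacturer will treat during about half of the UVA fractions. It keeps that investigator off the physician questionnaire but says nothing about causality grading.

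**Working it through.** The plan gives no figure to reproduce on this point. The check is to read the other passages against 9.1.1 under each possible meaning of the intervention.

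| Passage | If the intervention is packing only | If it also includes brachytherapy |
|---|---|---|
| 9.1.3.2, unlikely and unrelated grades | Cannot apply to an AE as regards packing | Can apply: related to brachytherapy, unrelated to packing |
| 9.1.6, first row of Table 3 | Empty | Has content if the row is read for packing |
| 9.1.5, regardless of relationship | Conflicts with 9.1.1 | Still conflicts for events related to neither |
| 7.3, no relatedness condition | Conflicts with 9.1.1 | Still conflicts for findings related to neither |

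The documents do not settle which column is right. Section 9.4 equates the study intervention with the type of packing, and 6.1 assigns only packing by arm. Against that, 9.1.1 allows a plural, 9.1.3.2 grades brachytherapy separately, and the rationale in 13.5 for redefining AEs says the definition covers standard-care as well as intervention-related events. The broad reading narrows the conflict but does not remove it.

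**What the filter could do (assumed values, not from the documents).** Let r be the true event rate, equal after both packings, and let s be the share judged at least possibly related.

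- Recorded rate = r × s, so the spurious difference = r × (s under one packing − s under the other).
- With shares of 80% and 50%: at r = 10%, 8% − 5% = 3 points; at r = 20%, 16% − 10% = 6 points; at r = 30%, 24% − 15% = 9 points. Swapping the shares reverses the sign.
- With equal shares the spurious difference is 0, but a real difference is multiplied by that share; at 50% it is halved.

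The assumed range therefore runs from 0 to 9 points in either direction. It shows the mechanism and is not an estimate for this trial.

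**What lies outside the conflict.** The primary endpoint is D2cc, which does not depend on AE capture. The stopping rule in 10.5 carries its own requirement that the event be at least possibly related to BrachyGel, so its definition is the same under either reading of 9.1.1.

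**Length of the recording window.** Under 9.1.5 it runs from completion of fraction 2 to 30 days after the last treatment for non-serious events. The synopsis puts fractions about 2 to 7 days apart. Three intervals give 3 × 2 = 6 to 3 × 7 = 21 days; adding 30 gives about 36 to 51 days if there are no delays.

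**The case against.** The strongest reply is that 9.1.5, Table 3 and 7.3 all point towards recording, so a reasonable site would enter everything. In addition, if brachytherapy counts as an intervention, nearly every pelvic event passes the threshold under either packing, and 9.1.3.2 says the study product is always to be suspected. The reach is also limited: the endpoint is secondary and for estimation, and 9.1.7 asks for serious events regardless of relationship. Much of this stands. It shows that filtering is not certain and might be slight. It does not show which rule a site must follow, and the protection for serious events is weaker than it looks because 9.1.2 rests on the AE definition.

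Four stronger readings are tempting, and the documents do not support them:

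- *Events judged unrelated never reach the database.* This assumes that 9.1.1 governs. It is the passage most recently redefined according to 13.5, but nothing says it overrides the others.
- *The 28 to 33% for milder bowel events in 2.3.1 is the event rate after each packing.* It is a per-patient frequency from a cohort. Here each participant receives both packings, and no per-packing rate is given.
- *Unrecorded events are lost for good.* Source records are retained (11.2.2) and monitoring reviews source documents (11.1.5). Recovery would be incomplete but not impossible.
- *An all-cause count by packing removes the bias.* With packing alternating every few days, events must still be assigned to a packing, so a rule is needed.

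**Conclusion.** The contradiction is definite. The AE definition depends on relatedness and several other current passages do not, and the plan neither ranks them nor defines the intervention. The consequence is conditional: where 9.1.1 is applied, the secondary AE comparison is restricted to events already attributed by an unblinded clinician, and capture may differ between UVA and AHN. The restriction is strongest if the intervention means packing alone and weaker if it includes brachytherapy. A reader might infer that the trial's safety comparison is biased for or against BrachyGel by a known amount. The documents give neither direction nor size, and the percentages in the illustration are assumptions. The point is worth correcting because it touches the only planned between-packing estimate of safety and needs only a change of text.

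**What to change.** 1. Amend 9.1.1 to agree with 9.1.5, 9.1.6 and 7.3: untoward events in the AE window are recorded regardless of relationship. Keep relationship to brachytherapy and relationship to packing as two separate recorded attributes.
2. Define the study intervention once, and check that 9.1.2 and 9.1.7 then cover the same serious events.
3. In 10.6, report all-cause and at-least-possibly-related AEs side by side by packing type, assigning each event to the most recent fraction before its onset date.

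The causality grades and the Table 3 rows already exist, so this is a text amendment. The cost is somewhat more non-serious AE entry over about 36 to 51 days per participant if there are no delays. The assignment rule is imperfect: with fractions 2 to 7 days apart, some early or late events will be credited to the wrong packing. Onset dates must also be reliable. The schedule in 13.1 marks AE review only at fractions 2 and 5 and the 30-day visit, while 8.1.2 and 9.1.5 call for it at each visit, so the amendment should align these too.
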